## **Ethical Considerations**

Written informed consent was obtained from the patient for publication and any accompanying images. A copy of the written consent is available for review by the Editor-in-Chief of this journal on request. Ethical approval for this study (Ethical

Committee 2022-OS-108) was provided by the Ethical Committee of Tishreen University Hospitals, Latakia, Syria on 18th September, 2022. In addition, the investigators ensured that the study conforms to the principles of the Declaration of Helsinki (last revised in 2013) and was conducted in accordance with the ICH Guideline for Good Clinical Practice.

## Statistical analysis

The Student's t-test, chi-square test with Yates' correction, Fisher's exact test, and Friedman test were used to compare the two groups. The statistic software SPSS 10.0 (SPSS, Inc., Chicago, IL) was used to analyze the data; p values below 0.05 were considered significant.

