## **Material and methods**

This study is a comparative retrospective study of 38 patients who had unstable distal clavicle fracture (Neer 2) featured in Figure 1. treated either with TBW technique (Figure 3 and 4) or A.O Hook plate fixation (Figure 2), and presented to the orthopedic department of Tishreen University Hospital, in Lattakia, Syria, between August 30, 2019 and August 30, 2022.

Data was extracted from the medical records of patients in the form of case sheets, discharge cards, x-rays, etc. The type of fracture was determined by Neer's classification.

We included patients who met the following criteria: Patients with unstable distal third clavicle fracture (Neer type 2), aged between 18 and 65 years old. Nevertheless, Patient who had open fractures, pathological fractures, fractures associated with brachial plexus or pulmonary or vascular injury, acromioclavicular joint disruption, and musculoskeletal disease that affects the joint, were excluded.

Preoperative shoulder x-rays in AP with (10-15) ° cephalic tilt (ZANCA View) and axillary view were taken. In addition, Basic lab tests were done for all patients on admission. We used A.O Hook plate with (4-7) holes, (3.5) mm screws and (12.15.18) mm of hook depth, and 2 Kirschner-wires of (2.0) mm and stainless steel wire of (18) gauge in the TBW technique.

Specified postoperative protocol was followed for all patients contained:

1. Arm immobilization with a sling inside the operation room under anesthesia.
2. I.V antibiotics and analgesic
3. A sterile wound dressing was applied routinely.

The surgical stitches were removed after (10-14) days after surgery, and all patients were subjected to the rehabilitation and physical treatment.

One examiner measured the outcome based on Constant-Murley score at 1.5-, 3-, 6-, 9-, and 12- month intervals. In this system, both subjective and objective clinical data are included, with a maximum score of 100 points, as the following: Pain (15 points), activities of daily living (20 points), range of motion of the shoulder (40 points), and muscle power (25 points) were evaluated.

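### No listed test makes full use of the five-visit Constant-Murley scores, and a single-visit t-test could be biased if attendance depends on both technique and recovery; a repeated-measures mixed model with a sensitivity analysis is better

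*Combined protocol and SAP*

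**What the plan says.** All references are to the combined protocol and SAP.

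- **Design (Material and methods).** "This study is a comparative retrospective study of 38 patients", treated "between August 30, 2019 and August 30, 2022". The number per technique is not given.
- **Data source (same section).** "Data was extracted from the medical records of patients in the form of case sheets, discharge cards, x-rays, etc".
- **Score (same section).** One examiner records the Constant-Murley score (maximum 100) "at 1.5-, 3-, 6-, 9-, and 12- month intervals".
- **Eligibility (same section).** "Patients with unstable distal third clavicle fracture (Neer type 2), aged between 18 and 65 years old", less a list of exclusions for other injury or disease. Neither a minimum follow-up nor a recorded score is required.
- **Analysis (Statistical analysis).** "The Student's t-test, chi-square test with Yates' correction, Fisher's exact test, and Friedman test were used to compare the two groups"; and "p values below 0.05 were considered significant". Beyond the software, that is the whole plan. It does not say which test serves which outcome, which visit is compared, or what happens when a visit is missing.

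No count of attended or missed visits appears anywhere.

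**The concern.** The chi-square and Fisher tests are for counts, so the t-test and Friedman are the only candidates for the score. The t-test at one visit ignores every earlier score of a patient who missed that visit. Friedman run over visits uses only patients with all five scores and asks whether scores change over time within patients. The t-test is therefore the only listed test that can compare the techniques on the score.

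In a chart review, scores exist where patients came back. Material and methods describes different recovery by technique: longer sling use and restricted motion until implant removal after tension band wiring (TBW), early full motion after the hook plate. Attendance that depends on both technique and recovery is therefore plausible, though not shown. If patients who do well stop attending more often after one technique, the 12-month t-test compares a selected remainder of that group with a fuller other group. That can create or hide a difference between techniques. The earlier recorded scores carry information about this, and the listed tests do not use it.

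**Working it through.** The plan gives no power, dropout or missing-data figure, so there is nothing to reproduce. From the documents come 38 patients, five visits, the 0.05 threshold and the list of tests. Assumed throughout are a 19/19 split (or large equal groups), the SD, the correlation between visits, the visit means and the dropout rules. The true 12-month difference is set to 0, and bias is hook plate minus TBW.

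**1. Patients each test can use.** If each visit is attended independently with probability p, a t-test at one visit keeps 38 × p and Friedman over five visits keeps 38 × p^5.

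| p | t-test at one visit | Friedman, all five visits |
|---|---|---|
| 0.95 | 36.1 | 38 × 0.774 = 29.4 |
| 0.90 | 34.2 | 38 × 0.590 = 22.4 |
| 0.80 | 30.4 | 38 × 0.328 = 12.5 |

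**2. What Friedman can detect.** It ranks the five visits within each patient. Adding a constant to all of a patient's scores leaves the ranks unchanged, so a steady difference between techniques cannot alter the statistic. In 2,000 simulated studies with complete data it rejected 5.45% of the time with no group difference and 5.45% with a 15-point difference. Its loss of patients is therefore real, but it is not a source of bias in the comparison of techniques.

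**3. Bias of the 12-month t-test when dropout follows earlier recorded scores.** The assumed inputs are 19 per group, visit means 50/65/78/85/88 and 1,200 replicates per row. Patients scoring 85 or more stop attending with the stated probability per visit.

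| SD | Correlation | Dropout hook/TBW | t-test bias | False positives |
|---|---|---|---|---|
| 10 | 0.5 | 0.3/0.1 | -0.90 | 6.4% |
| 12 | 0.5 | 0.3/0.1 | -1.24 | 5.3% |
| 10 | 0.7 | 0.5/0.1 | -2.32 | 9.0% |
| 12 | 0.7 | 0.5/0.1 | -3.09 | 11.1% |
| 12 | 0.7 | 0.5/0 | -3.86 | 14.1% |

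A random-intercept mixed model on the same data had bias of -0.13 to +0.10 and false positives of 4.1% to 5.2%. With equal dropout of 0.3/0.3 the t-test bias was -0.02. With mild dropout of 0.1/0.05 it was -0.36 (simulation standard error 0.16).

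**4. Direction and mechanism.** A second simulation used 20,000 per group, SD 12, and correlation either exchangeable 0.6 or AR(1) 0.7. The mixed model had an unstructured covariance.

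| Dropout depends on | t-test bias | Mixed-model bias |
|---|---|---|
| Technique only | -0.25, -0.04 | -0.30, -0.09 |
| Earlier score, hook plate only | -3.42, -2.86 | 0.10, -0.28 |
| Earlier score in both, different rates | +2.65, +1.75 | -0.03, -0.07 |
| Earlier score, opposite directions | -7.22, -5.30 | -0.33, -0.09 |
| Current unseen score, hook plate only | -3.93, -3.91 | -1.55, -2.25 |
| Current unseen score in both, different rates | +3.02, +2.61 | +1.34, +1.49 |
| Current unseen score, opposite directions | -8.09, -7.63 | -3.62, -4.69 |

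The technique-only row is simulation noise. The sign of the bias depends on the dropout rule. When dropout follows earlier recorded scores the model removes 90% to 99% of the bias; when it follows the unseen score it removes 38% to 61%.

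**5. Scale.** With SD 12 and 19 per group, all scored, the standard error of the 12-month difference is 12 × √(2/19) = 3.9 points. A bias of 0.5 to 3 points is then 0.5/3.9 = 0.13 to 3/3.9 = 0.77 standard errors. This is why the excess of false positives runs from negligible to about double the nominal 5%.

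**The case against.** The strongest reply is that nothing in the documents shows a missing score. Material and methods says that one examiner measured the outcome at the five times, and all 38 may have every score. That stands. If the 38 were chosen because their charts were complete, the model has nothing to recover, and only a check against all eligible operations would show the selection.

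Five stronger readings are tempting, and the documents do not support them:

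- **That the comparison is biased.** It could be. Without attendance counts no more can be said.
- **That attendance differing by technique is enough.** It is not; attendance must also depend on the score.
- **That Friedman's deletion of incomplete patients biases the technique comparison.** Friedman over visits does not make that comparison, even with complete data. Listing it among tests between two groups is the more basic fault.
- **That only TBW patients had reason to return.** Material and methods also schedules films up to 24 weeks without distinguishing technique, sends all patients to rehabilitation, and restricts heavy labour in both groups until union. The TBW reason ends at implant removal, which is undated. The direction of any bias is therefore a modelling choice.
- **That a mixed model removes most of the bias in any case.** This holds when missingness is explained by recorded scores. A further check used the step 3 means with SD 12, correlation 0.7 and dropout of 0.5/0.1 triggered by a current score of 85 or more. The random-intercept model still had bias of -1.53 (exchangeable) and -3.40 (AR(1)), against -5.25 and -5.71 for the t-test.

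It is also fair to say that the plan never assigns the t-test to the 12-month score; it might serve time to union. That leaves the score comparison unspecified, which is no defence of the plan.

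**Conclusion.** The concern holds in a limited form. No listed test makes full use of the repeated scores: the t-test uses one visit at a time, and Friedman over visits cannot compare the techniques at all. Whether this has biased anything is unknown, because missing visits are not reported.

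If attendance depends on technique and on earlier recorded scores, the 12-month t-test could be off by about 0.5 to 3 points in either direction. That range covers mild to fairly strong dropout. Bias near 4 points needs high-scoring patients to leave one group only, at a steep rate, and 5 to 7 points needs attendance to run in opposite directions with score in the two groups. All these figures rest on assumed SDs, correlations, dropout rules and group sizes.

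A mixed model on all recorded scores brings the bias close to zero under missing at random and only reduces it otherwise, so a sensitivity analysis is part of the remedy. This is a change the plan should make; the size of the problem is held with moderate confidence.

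**What to change.** 1. Report the number scored at each visit by technique, and state whether the 38 are all eligible operations in the window or only those with usable charts.
2. For the between-technique comparison of the score, replace the t-test and Friedman with one linear mixed model for repeated measures: technique, visit, technique-by-visit, and correlated visits within patient, fitted to all recorded scores. Report the 12-month difference with its 95% interval. An unstructured covariance over five visits has 5 × 6/2 = 15 parameters, which is many for 38 patients, so name a simpler fallback structure in advance.
3. Add a sensitivity analysis for missingness that depends on the unrecorded score. For example, shift the imputed scores by technique over a stated range and report where the conclusion changes.

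**Cost.** New SAP wording, a modest amount of analysis and a check that the named software release fits such models. No new patient contact is needed. The main model assumes missing at random. If no score is missing it gives the same 12-month answer as the t-test, so little is lost. It does not address confounding by the non-randomised choice of technique, which needs separate treatment.

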Furthermore, Radiological assessment was performed immediately after surgery, followed by evaluations at 3, 6, 12, and 24-week intervals to monitor healing progress and implant positioning. Recorded complications included infection, non-union, mal-union, pin migration, hardware impingement, and stiffness. The final outcome was assessed based on union status, time to fracture union, shoulder joint range of motion, ability to perform daily activities, and return to pre-injury status.

In the TBW group: The fixation method involved trans-articular fixation through the acromioclavicular joint, supplemented with an additional cerclage wire tension band for enhanced stability. Following surgery, the operated shoulder was supported with a triangular sling for a period of 4 to 6 weeks. Gentle mobilization was permitted once pain subsided, although full range of motion was limited due to pin impingement until implant removal.

In the Hook plate group: The operative procedure, as outlined in prior studies, involved creating a tunnel in the sub-acromial space posterior to the acromioclavicular joint and inserting the hook into this tunnel. If necessary, the plate was contoured to match the clavicle's shape, with careful consideration given to the appropriate depth of the hook. Dynamic compression was utilized to secure the plate in place. Following surgery, the shoulder was supported with a triangular sling for a period ranging from 2 to 4 weeks. Mobilization commenced at the earliest opportunity, typically resulting in full range of motion within three to four weeks. It is worth mentioning that across both groups, heavy manual labor was prohibited until evidence of solid fracture union was observed.

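### The plan specifies no analysis that compares the course of the five Constant-Murley scores between the two techniques

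*Combined protocol and SAP*

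**What the plan says.** Material and methods has one examiner record the Constant-Murley score "at 1.5-, 3-, 6-, 9-, and 12- month intervals". Range of motion carries 40 of its 100 points. No pre-operative score is listed.

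The same section describes different early courses of motion. For TBW, "the operated shoulder was supported with a triangular sling for a period of 4 to 6 weeks" and "full range of motion was limited due to pin impingement until implant removal". For the hook plate, the sling is worn for 2 to 4 weeks and mobilization starts early, "typically resulting in full range of motion within three to four weeks".

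The Statistical analysis section is the whole analysis plan. It states that "The Student's t-test, chi-square test with Yates' correction, Fisher's exact test, and Friedman test were used to compare the two groups", names the software (SPSS 10.0) and adds that "p values below 0.05 were considered significant". It does not tie any test to an outcome, a visit or a derived score. It lists no repeated-measures or mixed model, no technique-by-visit term and no change-score contrast.

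**The concern.** Five scores per patient can show whether a technique difference is lasting, early only or absent. The description of motion and sling time gives some reason to expect that the difference may vary over time. Of the listed tests, the two for counts do not apply to a score. The Friedman test ranks a patient's visits against each other. The t-test takes one number per patient, and the plan does not say which number.

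The likely default is one t-test per visit. Such tests show whether the groups differ at a given visit, but not whether the difference at one visit differs from that at another. Significance at 3 months without significance at 12 is not evidence of convergence, because a constant true difference can produce it by chance. At stake is any statement about how recovery with the two techniques compares over time.

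**Working it through.** The plan gives no effect size, SD, power or group split, so there is no figure of its own to reproduce.

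**Inputs from the documents:** 38 patients in all; five score visits; significance below 0.05.

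**Assumptions:** two-sided tests; 19/19 split; SD 12 at each visit; equal between-visit correlation ρ of 0.4, 0.6 or 0.8; a true technique difference of 0 to 14 points, the same at every visit unless stated.

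**1. What the Friedman test detects.** In simulation with a constant 1 SD technique difference and no time trend, it rejected in 5.1% and 5.0% within the two groups and in 5.4% pooled. With a shared time trend and no technique difference it rejected in 100%. It tests time, not technique or technique-by-visit.

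**2. One visit at a time.** The standard error of the difference is 12 × √(2/19) = 3.89. The critical t on 36 df is 2.028, so an observed difference must exceed 2.028 × 3.89 = 7.9 points. A true difference of 8 therefore gives about 52% power per visit. That is close to a coin toss, and so close to where verdicts at different visits disagree most.

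**3. False time patterns when the difference is constant** (20,000 simulated studies per setting; figures good to about one percentage point):

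| True difference | Significant at 3 months, not at 12 (ρ = 0.4/0.6/0.8) | Five verdicts mixed (range over ρ) |
|---|---|---|
| 0 | 5/4/3% | 12–20% |
| 4 | 11/9/7% | 27–47% |
| 8 | 19/15/11% | 43–74% |
| 12 | 10/8/6% | 25–43% |
| 14 | 5/4/3% | 13–22% |

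A t-test on each patient's 3-to-12-month change is falsely significant in 5% throughout. Separate runs used 19/19 and 13/25 splits and equal or autoregressive correlation. They gave mixed verdicts in 32–68% for constant differences of 0.5 to 0.8 SD, in 10–19% with no difference and in 10–23% at 1.2 SD. Direct tests of parallel courses stayed at 4.5–5.5%.

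**4. Power of a direct test if a gap of 8 at 3 months closes to 0 at 12.**
- SD of change = 12 × √(2(1−ρ)) = 13.1/10.7/7.6.
- Standard error = that × √(2/19) = 4.26/3.48/2.46.
- Noncentrality = 8/SE = 1.88/2.30/3.25.
- Power on 36 df is about 45/61/89%; simulation gave 44/60/89%.
- If the gap that closes is only 4 points, power is 15/21/35%.

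**5. Averaging the five visits.** The standard error relative to one visit is √((1+4ρ)/5) = 0.72/0.82/0.92. With a constant 8 points, power rises from 52% to 79/68/58%. If the gap closes as 8, 8, 5.3, 2.7, 0, the average difference is 24/5 = 4.8 points. Power on the mean is then about 38/31/26%, below the 52% at the 3-month visit alone.

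**The case against.** Several stronger readings are tempting, and the documents do not support them.

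- A reader might infer that no listed test could compare change between techniques. A two-sample t-test on each patient's change score could. The gap is that the plan does not specify this or any other such analysis.
- A reader might infer that p-values will be read visit by visit and faster recovery or catch-up claimed. The documents say neither. The aim in the Rational section is to compare clinical and radiological results and evaluate functional outcomes, with no stated time-course objective. The harm is possible, not announced.
- A reader might take the text as predicting that the scores converge. It describes motion and sling time, not the Constant-Murley score. The hook-plate milestone of three to four weeks falls before the first score visit at 1.5 months, and the time of pin removal is not given. The text therefore does not say that the difference changes between 3 and 12 months.
- A reader might treat the figures at 8 points as typical. They are near the worst case, since disagreement shrinks for both smaller and larger differences. The mixed-verdict figure also counts many patterns that nobody would call convergence, so the one-directional column is the fairer measure.
- A reader might infer that pooling visits always gains precision. It does so only if the difference is roughly constant (step 5).

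These objections limit the size and wording of the point. They do not supply the missing comparison, and dropping the Friedman test or naming one primary visit would not supply it either.

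**Conclusion.** The concern holds as a gap in specification with a concrete, better method available. The plan names no between-technique comparison of the five-visit course; Friedman cannot provide one, and visit-by-visit t-tests cannot show whether the technique difference changes.

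If visits are tested separately and the true difference is constant, a false early-only pattern arises in about 3% to 19% of studies over the assumed range. A direct test holds this kind of error at 5%. These figures rest on the assumed SD, split, correlations and differences, none of which the documents give. The change is worth making before any statement about the course of recovery, but nothing in the documents shows that such a statement is planned.

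**What to change.** In Statistical analysis, state that all five Constant-Murley scores are analysed in one repeated-measures or linear mixed model with technique, visit (categorical) and technique-by-visit, and patient as a random effect. Report the technique difference with its 95% CI at each visit. Claim earlier recovery or convergence only if the technique-by-visit test supports it, or one contrast fixed in advance, such as the change from 1.5 or 3 months to 12 months. If the Friedman test is kept, describe it as change over time within each group only.

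A t-test on each patient's change score is a simpler alternative that needs only a listed test. It is narrower than the five-visit interaction test, not equivalent to it. A five-visit mean should be added only if a roughly constant difference is expected.

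The cost is wording and one model on data already collected; confirm that the named software version can fit it. The downside is limited power with 38 patients (step 4). If the result is inconclusive, no time-course claim is made.

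### Student's t-test is named for two non-randomised groups with no stated sizes or SDs; if both differ, its 5% level is not protected, and Welch's version is a cheap safeguard

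*Combined protocol and SAP*

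**What the plan says.** The Statistical analysis section gives the whole method for comparing the groups in one sentence: "The Student's t-test, chi-square test with Yates' correction, Fisher's exact test, and Friedman test were used to compare the two groups". The test at issue is the first in that list, which opens with "The Student's t-test, chi-square test". The decision rule is "p values below 0.05 were considered significant". The section does not say which outcome each test is for, whether the t-test pools the variances, or whether the variances will be checked.

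Material and methods describes the design: "This study is a comparative retrospective study of 38 patients who had unstable distal clavicle fracture". Each patient was "treated either with TBW technique" or with a hook plate. The available text gives no group sizes and no SDs.

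The main numerical outcome appears in the same section: "One examiner measured the outcome based on Constant-Murley score". The score is taken at five visits from 1.5 to 12 months and has a maximum of 100, of which range of motion contributes 40. For the tension band group the section adds that "full range of motion was limited due to pin impingement until implant removal". Hook plate patients are said typically to regain full motion in 3 to 4 weeks.

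**The concern.** The pooled test uses one variance estimate for both groups. That is harmless if the groups are equal in size or have the same SD. It is not harmless if both size and SD differ. If the smaller group is the more variable, the standard error is too small and the test rejects too often. If the larger group is the more variable, the test is too strict and loses power.

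Nothing in a retrospective comparison forces a 19/19 split. The plan's own account of recovery makes unequal spread plausible. At the 1.5-month visit, hook plate patients may be close to the top of the motion component, which would compress their scores. Tension band patients may still be restricted to varying degrees. This is an inference from the text and shows no actual SD.

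At stake is the meaning of p below 0.05 for any continuous outcome compared by t-test. Without sizes and SDs, a reader cannot tell whether the true level is above or below 5%.

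**Working it through.** **Inputs from the document.** Total N = 38 (Material and methods); threshold 0.05 (Statistical analysis).

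**Assumptions, because the document is silent.** Two-sided testing; splits from 19/19 to 8/30, each summing to 38; SD ratio r = SD of the smaller group divided by SD of the larger group, from 0.5 to 2, with the larger group's SD set to 1.

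The plan has no sample-size or power figure to reproduce. Its only figure is the nominal 5%, which the pooled test does deliver when SDs are equal (5.0% at every split).

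**Step 1: hand check.** With n1 the smaller group and n2 the larger:

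- True variance of the mean difference: V = r²/n1 + 1/n2.
- What the pooled test estimates on average: E = [(n1−1)r² + (n2−1)]/36 × (1/n1 + 1/n2).
- Approximate type I error: P(|t with 36 df| > 2.028/√(V/E)).

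Putting numbers in:

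- 14/24, r = 2: V = 4/14 + 1/24 = 0.3274. E = (52 + 23)/36 × 0.1131 = 0.2356. V/E = 1.39; 2.028/1.179 = 1.72; error about 9.4%.
- 10/28, r = 2: V = 4/10 + 1/28 = 0.4357. E = (36 + 27)/36 × 0.1357 = 0.2375. V/E = 1.83; 2.028/1.354 = 1.50; error about 14.3%.
- 10/28, r = 0.5: V = 0.25/10 + 1/28 = 0.0607. E = (2.25 + 27)/36 × 0.1357 = 0.1103. V/E = 0.55; 2.028/0.742 = 2.73; error about 1.0%.
- 19/19: V/E = 1 for every r.

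**Step 2: simulation.** Normal data, no true difference, 4 million replicates per cell. Type I error of Student's pooled test, in percent:

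| Split | r = 0.5 | r = 1 | r = 1.5 | r = 2 |
|---|---|---|---|---|
| 19/19 | 5.3 | 5.0 | 5.1 | 5.3 |
| 14/24 | 2.4 | 5.0 | 7.8 | 9.8 |
| 12/26 | 1.6 | 5.0 | 9.0 | 12.1 |
| 10/28 | 1.0 | 5.0 | 10.4 | 14.7 |
| 8/30 | 0.6 | 5.0 | 11.9 | 17.7 |

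Welch's test, t = (difference in means)/√(s1²/n1 + s2²/n2) with Satterthwaite degrees of freedom, stays between 4.9% and 5.3% in all these cells. A mild imbalance of 16/22 gives Student 3.3% at r = 0.5 and 7.8% at r = 2 (200,000 replicates).

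**Step 3: price of Welch when SDs are equal.** With the effect set so that Student's test has 80% power, Welch loses 0.1 points at 19/19, 0.9 at 14/24, 1.7 at 12/26, 3.2 at 10/28 and 5.6 at 8/30.

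**Step 4: skewed scores.** The Constant-Murley score is capped at 100, so the shortfall from 100 was drawn from gamma distributions with equal means of 12 and SDs of 12 (smaller group) and 6 (larger group), 40,000 replicates. Student gives 10.5% at 14/24 and 15.1% at 10/28; Welch gives 7.4% and 9.3%. With equal groups of 19 and the same two SDs, both tests are at about 6% to 7%.

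**The case against.** The strongest case against is that the document shows no defect. A loss of control needs unequal sizes and unequal SDs together, and neither is documented. The passage on pin impingement speaks to the level of motion more than to its spread, and gives no SD ratio or direction. Pooling is the usual meaning of Student's test, but the section does not state it. The t-test is not assigned to the Constant-Murley score either; it could have been meant for age or time to union. Each of these points stands, and together they make the concern conditional.

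Two stronger readings are tempting. A reader might infer that unknown or unequal group sizes alone invalidate the test; the r = 1 column shows that they do not. A reader might also infer that the 5% level has in fact been breached. The document supplies neither quantity needed to say so.

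It is also fair to say that Welch is no complete cure. It reduces but does not remove the inflation with strongly skewed scores, and it does nothing about confounding from non-random choice of technique, which is the larger issue in this design. These points limit what the change achieves. They are not reasons to prefer the pooled test, whose level depends on quantities the plan does not give.

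**Conclusion.** The point holds in conditional form. As written, the named test does not guarantee its 5% level if the groups differ in both size and SD. Across the assumed splits from 14/24 to 10/28, with the smaller group having 1.5 to 2 times the SD, the true level would be roughly 8% to 15%. With the smaller group having half the SD it would be roughly 1% to 2.4%. With equal SDs or a 19/19 split, it is about 5.0% to 5.3%. These figures rest on normal data, two-sided testing, N = 38, and assumed splits and SD ratios. The plan's description of recovery makes unequal spread plausible but does not show it. This is an optional improvement, worth making because it is cheap.

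**What to change.** In the Statistical analysis section, name Welch's unequal-variance t-test for continuous outcomes compared by t-test, and say which outcomes those are. Report the size of each group, the SD in each group, and the mean difference with its Welch 95% CI. If Student's test has already been run, show the Welch result beside it and say that it was added later.

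The change is a line of wording and a re-run on data already held. It needs no new data and no change to care. The downside is the loss of power in Step 3 if the SDs are in fact equal: negligible near equal groups, about 3 points at 10/28 and 5 to 6 points at 8/30.

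### Yates-corrected chi-square and Fisher's exact test are both listed with no rule for choosing between them; at 38 patients they can disagree at 0.05, both are conservative, and no effect estimate or interval is planned

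*Combined protocol and SAP*

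**What the plan says.** Material and methods describes a "comparative retrospective study of 38 patients", who were "treated either with TBW technique (Figure 3 and 4) or A.O Hook plate fixation". The number in each group is not stated.

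The binary outcomes are union status and six complication types: "Recorded complications included infection, non-union, mal-union, pin migration, hardware impingement, and stiffness".

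Statistical analysis names four procedures together: Student's t-test, the "chi-square test with Yates" correction, and Fisher's "exact test, and Friedman test were used to compare the two groups". It does not match any test to an outcome and gives no condition, such as an expected-count threshold, for using one 2x2 test instead of the other. The only decision rule is "p values below 0.05 were considered significant". Sidedness, expected rates, power, effect measures and confidence intervals are not mentioned.

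**The concern.** Two tests suit the same kind of table, and nothing fixes which is used. The data come from existing records, so the test could be chosen after the table is seen. If the two can fall on opposite sides of 0.05, the reported conclusion may depend on that choice.

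Both tests are also known to be conservative in small samples. A test that rejects well below its nominal 5% gives up power, and this study has little to spare. With a bare p value and no interval, a non-significant complication comparison tells the reader nothing about how large a difference remains compatible with the data.

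**Working it through.** The plan has no sample size or power figure to reproduce, so I enumerated every possible 2x2 table.

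**Inputs.** From the documents: N = 38 and alpha = 0.05. Assumed: two-sided tests; splits 19/19, 18/20, 17/21, 16/22, 15/23, 14/24, 12/26 and 10/28; event rates as shown below.

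**Formulas.** For events a, b and non-events c, d in arms of n1 and n2:
- Yates: X² = N(|ad − bc| − N/2)² / [(a+b)(c+d)·n1·n2], referred to chi-square on 1 df.
- Fisher: the sum of hypergeometric probabilities no larger than that of the observed table.
- Boschloo: Fisher's p value used as the statistic, with the rejection probability maximised over the common event rate.
- True size or power: the sum of Bin(a; n1, p1)·Bin(b; n2, p2) over tables with p<0.05. Size sets p1 = p2.

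**One table by hand, 0/19 v 5/19.**
- Yates: |0×14 − 5×19| = 95; 95 − 19 = 76; X² = 38×76²/(5×33×19×19) = 219,488/59,565 = 3.685; p = 0.055.
- Fisher: 2×C(19,5)/C(38,5) = 2×11,628/501,942 = 0.046.
- Boschloo: p = 0.023.

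**How often they disagree.** At 19/19, 8 of 400 tables are discordant; the other splits give 10 to 18 each. Fisher is the significant test every time. Another example is 0/16 v 6/22, with Fisher 0.030 and Yates 0.068. Discordant tables with all expected counts of at least 5 exist in every split except 10/28. At 19/19 there are four, all with 0.0489 v 0.0503. The probability of observing a discordant table at 19/19 is under 1% when the rates are equal (5% to 50% checked), 1% for 10% v 40%, 7% for 5% v 30% and 16% for 0% v 20%. At 14/24 it is 12% for 5% v 30% and 11% for 10% v 40%.

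**True size.**

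| | Yates | Fisher | Boschloo |
|---|---|---|---|
| 19/19, maximum over all rates | 2.3% | 2.8% | 4.5% |
| 19/19, common rate 5% | 0.02% | 0.15% | 0.2% |
| 19/19, common rate 10% | 0.3% | 1.1% | 1.5% |
| Maximum, range over the eight splits | 2.0-2.6% | 2.8-3.8% | 4.5-5.0% |

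**Power.**

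| | Yates | Fisher | Boschloo |
|---|---|---|---|
| 5% v 30%, 19/19 | 34% | 41% | 51% |
| 5% v 30%, 14/24 (5% in the arm of 14) | 24% | 36% | 48% |
| 10% v 40%, 19/19 | 45% | 46% | 58% |
| 0% v 20%, 19/19 | 16% | 33% | 33% |

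**How much is due to the test.** For 10% v 40% at 19/19, Fisher misses 100 − 46 = 54% of such differences and Boschloo misses 100 − 58 = 42%. The choice of test accounts for 12 points. The other 42 remain because the sample is small.

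**What an interval adds.** With 0 events in 19, the upper limit of the two-sided 95% Clopper-Pearson interval is 1 − 0.025^(1/19) = 17.6%. An arm with no recorded events is therefore still compatible with a true rate of about one in six.

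**The case against.** A reader might infer that both tests are meant for the same tables. The section does not say so. A common convention sends tables with small expected counts to Fisher and the rest to chi-square. Under that convention 0/19 v 5/19 and 0/16 v 6/22 (smallest expected counts 2.5) would both go to Fisher, with no conflict. This stands in part: the defect is the missing rule, not a stated double analysis. But the convention is not written down, and discordant tables remain above the threshold of 5 in seven of the eight splits.

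A reader might also infer that the listed tests are why real complication differences would be missed. They are a contributing cause; the main one is 38 patients.

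Fisher's test is valid, since it never exceeds 5%, and preferring an unconditional test to it is partly a matter of taste. Boschloo does not cure conservatism for rare events: its size at 19/19 is 0.2% at a 5% rate and 1.5% at a 10% rate. It adds nothing to Fisher for 0% v 20% at 19/19. That pattern is relevant here, because Kirschner wires are described only for the tension band group, so pin migration should not arise with the hook plate. All of this stands, and it is why Boschloo is offered as an option and not required.

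Six complication types and union, each tested at an unadjusted 0.05, make a less conservative test not wholly free of cost across the set. That is a fair caution. It does not favour Yates, which found no table significant that Fisher missed.

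**Conclusion.** The point holds as a missing selection rule combined with a poor choice of one test. At N = 38, in all eight assumed splits, Yates rejects only where Fisher also rejects, while Fisher already keeps its error rate below 5% (maximum 3.8%). The Yates-corrected test therefore offers no protection that is needed, and it costs from about 1 point of power (10% v 40%, 19/19) to about 16 points (0% v 20%, 19/19) against Fisher. Disagreement across 0.05 is confined to borderline tables, but it is not negligible when one arm has few or no events.

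The documents do not support saying that Fisher's test is wrong, that both tests are applied to one table, or that the investigators intend to read p>=0.05 as similarity. The lack of any planned effect estimate or interval only leaves that misreading open.

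The sizes given rest on two-sided testing and on assumed arm sizes and event rates, none of which the documents state. This is a cheap improvement that should be made; it does not invalidate the analysis.

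**What to change.** In Statistical analysis, delete the Yates-corrected chi-square and name one exact test, with its sidedness, for every 2x2 comparison of complications and union. Fisher's exact test is the minimum. Boschloo's test is a more powerful option that keeps the 5% level. Fisher mid-P is another option but does not strictly guarantee that level: its maximum size reaches about 5.4-5.5% at 12/26.

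Report each comparison as events over patients in each group, with the risk difference and a 95% CI (for example Newcombe's). State that p>=0.05 will not be read as no difference.

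The cost is a few sentences and a re-run of the binary comparisons on data already held. Boschloo's test may need software other than the package named and is less familiar to readers. None of this makes up for the small sample; the intervals will be wide, and the report should say so.
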